# Exclusion criteria:

- Any child without parental permission or assent
- Any adult from the aforementioned categories without a signed informed consent form

Inclusion/exclusion criteria have been previously determined to be appropriate for minors – in this case, school children.

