#### Response:

We are using a crossover pre/post study design where seven after-school programs would receive the intervention in years 1 and 2 and seven schools would serve as matched comparison sites. During year two, the next seven schools would receive the intervention. This tiered approach begins with an initial assessment of the playgrounds to ensure that designs include the research-based elements of balancing, brachiating, climbing, spinning, sliding, and swinging. During years 1 & 2, Healthy School Staff will be trained with the xxx curriculum and the children will be trained as Peer Leaders (Fall Semesters 2022 and 2023) who are enrolled in the after-school program who then become peer leaders for all children during recess at their school.

Assessments include Physical, Social and Emotional Health Assessments administered fall and spring semesters of both years to track student behaviors. Assessments of the after-school setting will be conducted by Xplore program leaders on paper and include observations of all students attending Xplore programs. Assessments during recess would be conducted by recess aides/healthy school staff and would include a random sample of 25 students at recess. No identifying information will be recorded. Assessments will take approximately 5-10 minutes to complete. A copy of the assessment is included (K-6 Assessment).

We will ask the Healthy School Staff to complete a survey each fall and spring semester to learn about their perceptions of the training and playground activities. The survey will take approximately 5-10 minutes to complete. A copy of the staff assessment is included (Healthy School Staff Survey). Healthy School Staff may also be asked to participate in a 30-minute interview each spring semester.

We will ask students to complete a short survey about their physical, social, and emotional health and perceptions of the play activities in the program twice a year. The survey will take approximately 5-10 minutes to complete. A copy of the student assessment is included (Student Survey).

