- 11.4 No identifying information will be stored, so extra protection for highly sensitive material is not warranted.
- 11.5 We will not obtain any audio or video recordings.
- 11.6 Consent and assent forms will be secured in a manilla envelope in a locked file cabinet in a locked room. They will be kept for 5 years. These forms will be kept separate from the rest of the data from the study.

11.7 We will use a master list of student IDs that will not be tied to any identifiable information. Any identifiable information included in this master list will be destroyed (deleted or shredded) as soon as the data are linked. These IDs will be used to link accelerometer devices to individual demographics such as sex and school.

11.8 No identifying information will be included in the research.

11.9 No secondary data will be utilized in this research.

11.10 We will not include any data covered under FERPA.

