A cluster randomized controlled trial of an after-school playground curriculum intervention to improve children's physical, social, and emotional health: Study protocol for the PLAYground project

NCT ID not yet assigned

Date: June 20, 2022

Statistical Analysis Plan

Data analysis

Intervention effects on the primary trial outcomes (at each follow-up time point) will be assessed using general linear mixed effects models to account for the clustering of individual measurements within schools. These will include fixed effects for treatment group (intervention vs control), time (baseline and follow-up), and interaction term (intervention x time); include school as a random effect; and be adjusted for covariates related to the outcome (eg, student sex, age). Analyses related to physical, social, and emotional health will be performed with the child (nested within a school) as the unit of analysis. Analysis related to attendance and behavioral change will be performed with the school as the level of analysis. Separate analyses will be performed at each follow-up time point. Schools will be included in analyses if they meet at least 80% adherence to the protocol.

Secondary implementation outcomes will be assessed using descriptive statistics for Healthy Staff and Student survey data (appropriateness and feasibility) and data from monthly observations (fidelity and sustainability). Frequencies, means, and standard deviations will be calculated to describe the distributions, measures of central tendency, and dispersion of item responses. Data from Healthy Staff and Student interviews will be analyzed using a matrix analysis to summarize and organize data in alignment with Proctor's dimensions (adherence, exposure/dose, quality of delivery, component differentiation, and participant involvement), and content analysis to identify salient themes for each school, by school-level income, and collectively among intervention school groups. We will utilize a deductive approach, but allow for additional themes to emerge.

Sample size calculation

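### As written, the observed physical, social and emotional assessments have no stated link to a child's earlier record, age or sex, and the SAP does not say whether they feed its child-level model

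*Protocol*

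**What the plan says.** Protocol section 7 (Study Procedures, Response) describes "Physical, Social and Emotional Health Assessments administered fall and spring semesters of both years to track student behaviors". After-school program leaders complete them on paper, and these forms "include observations of all students attending Xplore programs". At recess, aides or healthy school staff complete them, and that set "would include a random sample of 25 students at recess". The same paragraph adds: "No identifying information will be recorded".

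The same section gives each child participant a non-identifying study ID for use during the study, and collects gender, age and race/ethnicity for student participants only. Section 4 excludes "Any child without parental permission or assent". Section 11.7 names one use for the IDs, linking accelerometers to demographics, and says that identifiable information in the master list "will be destroyed (deleted or shredded) as soon as the data are linked".

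The SAP (Data analysis) says that analyses of physical, social and emotional health "will be performed with the child (nested within a school) as the unit of analysis". The model has group, time and their interaction, school as the random effect, and covariates for which sex and age are the examples. No instrument is named.

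**The concern.** The three domains on the observation form are the three that the SAP analyses per child, so the form is a natural candidate for the outcome. Yet nothing in the documents puts the study ID, age or sex on it. There are three consequences if it is used.

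- **Pairing.** A child's fall and spring ratings would have to be treated as ratings of different children. Protocol section 8 says all participants take part in both years, so the programme children are a cohort and the pairing exists to be used.
- **Covariates.** Age and sex are collected for participants only. Other attendees and most recess pupils have no stated source for either.
- **Population.** The forms include children whom the exclusion rule leaves out, so the estimate would not describe the enrolled sample.

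Pairing that is not recorded at collection cannot be recovered afterwards.

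**Working it through.** The plan gives no figure for this point. The nearest is the detectable effect of 0.370 in the SAP (Sample size calculation). From the plan's inputs (7 schools and 147 children per arm, 21 per school, ICC 0.05, 80% power, alpha 0.05 taken as two-sided) the design effect is 1 + 20 × 0.05 = 2.0, and the detectable effect is (1.960 + 0.842) × √(2 × 2.0/147) = 0.462. So 0.370 is not reproduced. It would be reached with about 36% of variance explained, since 0.462 × √(1 − 0.36) = 0.370; a baseline correlation of about 0.6 would do this. The plan states no such gain, and a gain from a child's own baseline needs linked records. The sample-size figure is otherwise a separate matter.

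**Who is observed.**
- After school: 420 enrolled across 14 programmes, or 210 per arm if split evenly. Participants: 0.70 × 420 = 294, or 147 per arm. Non-participants: 420 − 294 = 126, which is 126/420 = 30%.
- Recess, assuming 25 per school drawn afresh at each wave from all 610 pupils (average enrolment): participants expected in a draw are 25 × 21/610 = 0.86, and children shared by two draws are 25 × 25/610 = 1.0.

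**Precision of one baseline-to-follow-up contrast.** Outcome variance is set to 1 and ICC to 0.05 (SAP). School autocorrelation 0.8 and within-child correlation ρ = 0.3, 0.5, 0.7 are assumptions. With n children per arm at each wave,

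Var = 2 × [2(0.05)(1 − 0.8)/7 + 2(0.95)(1 − ρ)/n] = 2 × [0.02/7 + 1.9(1 − ρ)/n].

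Unlinked records take ρ = 0:
- n = 147: √(2 × [0.00286 + 0.01293]) = 0.178
- n = 210: √(2 × [0.00286 + 0.00905]) = 0.154

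Linked records exist only for the 147 participants:

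| ρ | Linked SE, n = 147 | Unlinked excess, n = 147 | Unlinked excess, n = 210 |
|---|---|---|---|
| 0.3 | 0.154 | 15% | 0% |
| 0.5 | 0.137 | 30% | 13% |
| 0.7 | 0.116 | 53% | 33% |

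The last column fits forms that cover all attendees. The column before it applies if only 147 unlinked records per arm are used. At ρ = 0.3 the extra attendees exactly offset the lost pairing, because 147/(1 − 0.3) = 210.

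**The case against.** The strongest reply is that the SAP never assigns these forms to the child-level model. The protocol also says "We will ask students to complete a short survey about their physical, social, and emotional health", twice a year, and accelerometers are worn by participants who have IDs. If those two supply the outcomes, the anonymous observations are a setting-level measure and there is no conflict. This stands, and it is why the point is conditional. It does not dispose of the point: the SAP leaves the choice open, an ID on the survey is at most implied, and the accelerometer covers activity only.

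A reader might infer that the forms cannot feed the SAP model at all. The documents do not support that. The stated model has a random effect for school and none for the child, so group by time can be fitted to unlinked records as repeated cross-sections, and sex and age are only examples of covariates. The assessment form is not among the documents, and recording age, sex or a non-identifying ID on it would not contradict the protocol. For participants, then, the gap is an unwritten step, not a prohibition. For children without an ID or collected demographics, it remains.

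Two further inferences also go too far. No section pools recess pupils with the after-school cohort, and a school-wide recess sample suits the aim in section 2 of reaching all pupils through peer leaders; few participants among the 25 is no defect in such a measure. And section 11.7 ties destruction of identifiers to completion of linkage. It does not say that this happens before the last wave, only leaves the wave unstated.

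**Conclusion.** The point holds in conditional form. If the observed assessments supply any child-level primary outcome, then followed as written they do so without within-child pairing, without a stated source of age and sex, and on a population of which about 30% is not enrolled (after-school forms) or nearly all is not enrolled (recess forms). The documents do not settle whether they are the source.

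The loss of precision is uncertain: 0% to 33% on the standard error if all attendees are used, and 15% to 53% if 147 per arm are used. A reader might take the upper range as the cost, but it sets aside the extra attendees whom the forms cover. Both ranges rest on the assumed school autocorrelation and within-child correlations, an even split of attendees between arms, and the same numbers at each wave. At within-child correlations below 0.3, limiting the model to linked participants would cost precision against using all attendees. The case for linkage would then rest on the covariates and the population.

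**What to change.** - In the SAP, name the instrument for each primary outcome (observed assessment, student survey or accelerometer), and say whether its analysis is a cohort or a repeated cross-section.
- Add the non-identifying study ID to the after-school form for consented children, and use only those records in the child-level model. Age and sex then come from the demographic data already planned.
- Add a child random effect, or adjust follow-up for the child's own baseline. Without one of these, an ID on the form brings no gain in precision, because the stated model treats a child's two records as independent given school.
- State in section 11.7 that the ID key is kept until the last wave has been linked.
- Analyse the anonymous recess sample separately as a repeated cross-section summarised by school and wave, and label it a school-wide spill-over outcome.

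The cost is one field on a paper form, a model term, and a few sentences in the protocol and SAP. The practical burden is that leaders must look up an ID for each consented child at each wave. The form needs changing before the first fall assessment.

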#### IRB: 8. Compensation

8.1 Report the amount and timing of any compensation or credit to participants.

8.2 Identify the source of the funds to compensate participants.

8.3 Justify that the compensation to participants to indicate it is reasonable and/or how the compensation amount was determined.

8.4 Describe the procedures for distributing the compensation or assigning the credit to participants.

#### TIPS for streamlining the review time.

- ✓ If partial compensation or credit will be given or if completion of all elements is required, explain the rationale or a plan to avoid coercion
- ✓ For extra or course credit guidance, see "Research on educational programs or in classrooms" on the following page:
  - https://researchintegrity.asu.edu/human-subjects/special-considerations.
- ✓ For compensation over \$100.00 and other institutional financial policies, review "Research Subject Compensation" at:

# https://researchintegrity.asu.edu/human-subjects/special-considerations for more information.

#### Response:

We have incentives for principals, teachers and students.

**Incentives**: Students: \$10 per student per semester x 25 per school x 14 schools

Incentives: Program Leaders: \$50 gift card per leader per semester x 5 per school x 14 schools

Incentives: Healthy School Leaders: \$50 gift card per leader per semester x 5 per school x 14 schools

Note that all participants are participating in both year 1 and 2 either as a comparison or program participant.

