#### Response:

2. This project uses the **evidence-based Play On! program to promote social, emotional, and physical health of children** through active and inclusive play. The Play On! program will be **implemented during the after-school enrichment programs** at 14 elementary schools in the xxx School District using a tiered approach that begins with a playground design assessment and a training for after-school coordinators and healthy school staff (recess aides, physical education teachers, and healthy school managers), and extends to include trainings for students to become peer leaders to facilitate active and inclusive play during recess. This 'train the trainer' model allows for great reach as the students attending the 14 after-school programs will spread their knowledge and skills to all students attending the schools during recess.

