#### Response:

## Inclusion criteria:

Children:

- Children in after school programs in XXX Schools (N=294 students at 14 schools)
- Children range in age from 5-13 (grades Kindergarten to 6th grade)
- We will not include any other special population (adults who are unable to consent, prisoners, or economically/educationally disadvantaged individuals)

Adults (Healthy School Leaders):

- after-school program leaders in xxxc Schools
- Recess Aides in schools with after school programs in xxx Schools
- Active, Healthy & Safe team members in schools with after school programs in xxx
- Healthy School Managers in schools with after school programs in xxx Schools
- Physical Education teachers in schools with after school programs in xxx Schools:
- Principals in schools with after school programs in XXX Schools

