#### Response:

We expect to recruit 294 children in grade three to six from 14 schools in xxx School District (about 21 students per school). We expect to recruit about 150 adults (~10 adults per school).

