The average enrollment of schools in the study district is 610 students. The average enrollment in all 14 after school programs across schools in the study district is 420 students. Using an estimate of a 70% participation rate among after-school programs and assuming 20% loss-to-follow-up, a sample of 7 intervention and 7 control schools will provide a sample of approximately 294 students (147 intervention and 147 control) at follow-up. Assuming an intra class correlation coefficient of 0.05 with 80% power and an alpha of 0.05, the sample will be sufficient to detect an effect size of .370, similar to other school-based PA interventions reporting small overall effects.

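### The plan makes no provision for sixth graders leaving after year 1, so its single follow-up sample of 294 does not describe the year 2 follow-ups

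*Protocol*

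**What the plan says.** Protocol section 2 places the programme in "14 elementary schools in the xxx School District". Section 4 gives the children's range as "Children range in age from 5-13 (grades Kindergarten to 6" (that is, up to sixth grade). Section 5 is narrower: "We expect to recruit 294 children in grade three to six from 14 schools", about 21 per school.

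Section 7 runs over two school years, with peer-leader training in "Fall Semesters 2022 and 2023" and assessments each fall and spring. It plans accelerometry four times on the student participants of the seven intervention schools (n=147). At the other seven schools (n=147) accelerometry is limited to their control year. Students also complete a survey twice a year. Section 8 adds "Note that all participants are participating in both year 1 and 2 either as a comparison or program participant".

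The SAP's sample size section starts from 420 children enrolled in the 14 programmes. It applies 70% participation, "assuming 20% loss-to-follow-up", and reaches about 294 children (147 per arm) at follow-up. With an ICC of 0.05, 80% power and alpha 0.05, it states a detectable effect of 0.370. Its data analysis section says "Separate analyses will be performed at each follow-up time point".

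**The concern.** A child in sixth grade in 2022-23 will normally have left an elementary school by fall 2023. For that grade, participation in both years and four measurements on the same 147 children are not possible. Neither document describes following leavers, enrolling new children in year 2, or restricting year 2 analyses to lower grades.

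This matters because the SAP analyses each follow-up on its own but gives one sample and one loss, tied to no wave. A reader would take 294 as the number available in year 2. The year 2 sample of individually followed children would be smaller than that, and the missing children would be the oldest, so year 2 results would describe a younger group than was enrolled. If leavers were replaced instead, year 2 would compare partly different children with those measured at baseline.

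**Working it through.** **Inputs.** Enrolment 420, participation 70%, loss 20%, ICC 0.05, power 80%, alpha 0.05, seven schools per arm (SAP, sample size calculation). Grades 3-6 (Protocol section 5) or K-6 (section 4). Three assumptions are mine: a two-sided test, equal grade sizes, and sixth as the last grade.

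**Step 1: the plan's own figures.** 420 × 0.70 = 294, so the stated follow-up sample has had no loss removed. Section 5 gives the same 294 as the number to recruit. With the loss taken off, 294 × 0.80 = 235.2, or 16.8 per school.

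The detectable effect, by normal approximation, is (1.96 + 0.84) × √(2 × DE / n). Here n is children per arm, m is children per school, and DE = 1 + (m − 1) × 0.05.

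- 294 children: n = 147, m = 21, DE = 2.00, effect 0.462.
- 235 children: n = 117.6, m = 16.8, DE = 1.79, effect 0.489.

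The stated 0.370 is not reproduced from its own inputs at either size.

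**Step 2: departure of sixth grade alone.**

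- Grades 3-6: one quarter leaves, 294 × 0.25 = 73.5, so 220.5 remain.
- K-6: one seventh leaves, 294 / 7 = 42, so 252 remain (14.3% lost).

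For the 147 accelerometer participants in the intervention schools, 147 × 0.75 = 110 or 147 × 6/7 = 126 would still be there in year 2, before any other loss.

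**Step 3: departure plus a further 20% ordinary loss.**

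- Grades 3-6: 220.5 × 0.80 = 176.4 (40% lost); n = 88.2, m = 12.6, DE = 1.58, effect 0.530.
- K-6: 252 × 0.80 = 201.6 (31% lost); n = 100.8, m = 14.4, DE = 1.67, effect 0.510.

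**Step 4: what grade exit itself adds.** The proper comparator is the 235 children left after ordinary loss, at 0.489. Grade exit adds 0.530 − 0.489 = 0.041 or 0.510 − 0.489 = 0.021.

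**Step 5: sensitivity to the grade mix.** For sixth-grade shares from 5% to 35%, with a further 20% loss, total loss runs from 24% to 48% and the detectable effect from 0.496 to 0.554.

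**The case against.** Several points on the other side are sound.

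- **Last grade.** No section says that sixth is the last grade at these schools. It is inferred from the word elementary and the K-6 range, so the point must stay conditional.
- **Purpose of the section 8 note.** It sits under an incentive budget and may mean only that both groups of schools are active in both years. That softens the sentence, but section 7 independently plans four measurements on the same 147 children.
- **The 20% figure.** A reader might infer that 20% loss is impossible in year 2. The documents do not support that. With equal K-6 grades, departure takes 14.3%, and total loss stays within 20% if ordinary loss among the rest is at most 1 − 0.80 / (6/7) = 6.7%. Section 12 asks for child assent in grades 3-6, which fits younger children also being enrolled. The SAP does not tie the 20% to year 2, nor say that it excludes grade exit. Only with equal grades 3-6 does departure alone exceed it.
- **The detectable effect.** A reader might attribute the whole distance from 0.370 to 0.53 to sixth graders leaving. Most of it comes from the loss never being removed and from 0.370 not reproducing, which are separate errors.
- **The trial's main contrast.** A reader might infer that this contrast is damaged. The other seven schools receive the intervention in year 2 (sections 6 and 7), so the concurrent comparison lies mainly in year 1, before anyone leaves. A two-arm detectable effect therefore means little in year 2.
- **Other outcomes.** The after-school and recess observations record no identifiers and sample whoever is present. Attendance and behaviour are analysed by school. Neither shrinks because a grade moves on.

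What remains is that the individually followed measures in year 2 have no stated cohort, loss or sample size.

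**Conclusion.** The point holds in a limited form. If sixth is the last grade, the statements on participation in both years and on four measurements of the same 147 children fail for the sixth graders of 2022-23. The single figure of 294 then does not describe the year 2 follow-ups for accelerometry and the student survey. Under equal grade sizes and a further 20% ordinary loss, about 176 (grades 3-6) or 202 (K-6) children would remain. The cost in detectable effect is modest, about 0.02 to 0.04 above the 0.49 that a correct 20% loss gives. These sizes rest on an assumed grade mix and should be read as a range. The year 1 comparison stands. The defect is a missing definition and an unsupported year 2 sample size, to be corrected before year 2 results are analysed.

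**What to change.** - In Protocol sections 7 and 8, say that children in sixth grade at enrolment contribute individual data in year 1 only (or, if the schools go beyond sixth grade, say so).
- Reconcile the grade range in sections 4 and 5.
- In the SAP, state whether year 2 is a closed cohort (children below sixth grade at enrolment) or admits new children. If it admits them, say how they enter the analysis.
- Restate expected loss and sample size by wave from the actual grade mix, not from the equal-grade figures used here.
- Tie the powered contrast to the year 1 follow-up and give year 2 precision separately. When recalculating, take the 20% off the 294 and rederive the detectable effect.

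The cost is wording and one recalculation. The downside is that the stated year 2 sample becomes smaller.
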